#### 2.4.4 Analyses of efficacy endpoints

All efficacy analyses will be performed based on the ITT approach that will include events occurring, for a given patient, from the date of randomization to their date last known alive, including events that occur after the patient has discontinued the study IMP.

##### 2.4.4.1 Analyses of primary efficacy endpoint

The analysis of the primary efficacy endpoint will be the comparison between the two treatments using a Wald test stratified by region (North America, Latin America, Western Europe, Eastern Europe, and rest of world) and LVEF (<50%, ≥50%). This primary comparison will be a 2-sided test at the 0.05 type 1 error level for the following hypothesis:

H0: HR=1 versus H1: HR ≠1

The estimates of the hazard ratio (HR) and corresponding 2-sided 95% confidence interval (CI) will be provided by a marginal Cox proportional hazard model stratified by region and ejection fraction, with non-cardiovascular (non-CV) death treated as a competing event. By using a robust sandwich covariance matrix estimate, the model allows for the possibility of multiple events within a given patient. If a given patient has more than one event on a given day, the event times will be varied by 0.1 day so that every event time is unique.

To determine whether the treatment effect on the primary endpoint is different before and after 240 days (the end of the window for up-titration of dose), a marginal proportional hazards model that allows the treatment HR to vary before and after 240 days will be compared with the model in which the treatment HR is assumed constant over time, to test whether a nonconstant HR provides a better fit to the observed data.

As a sensitivity analysis, an on-treatment analysis will be performed for the primary endpoint, using the same method above but only including events through 30 days after last dose. Another on-treatment sensitivity analysis will include only events through 7 days after last dose.

The cumulative incidence function (CIF) will also be constructed to estimate the primary efficacy endpoint rate by treatment group. The absolute risk reduction (ARR) will be estimated by the difference between treatment groups in the number of events per 100 patient-years of follow-up. Results will be provided for both the primary efficacy endpoint overall and its individual components (CV death, HHF, urgent HF visit). In addition, a figure summarizing the numbers of first and subsequent events will be constructed for the primary endpoint. Bars for sotagliflozin and placebo will be provided for the numbers of first events, second events, and a category of “third and subsequent events.” Within each bar the number of CV death, HHF, and urgent HF visit events will be separated by color.

Proportional hazards model for the primary endpoint will be constructed for subgroups defined by the following:

- LVEF in two categories (<50%, ≥50%)
- LVEF in three categories (<40%, ≥40% <50%, ≥50%)
- Region in three categories (The Americas, Europe, Rest of the world)
- Age (<65, ≥65)
- Gender (male, female)
- Race/ethnicity (white, black, Hispanic, Asian, other)
- Baseline eGFR (<60 mL/min/1.73m^2, ≥60 mL/min/1.73m^2)
- Baseline BMI (<30, ≥30 kg/m^2)
- NYHA Class (II, III, IV)
- NT-proBNP (≤Median, >Median)
- MRA at Baseline
- GLP-1 receptor agonist at Baseline
- Sacubitril-valsartan at Baseline
- ICD/CRT at Baseline
- Insulin at Baseline
- Atrial fibrillation or flutter at baseline
- Left ventricular hypertrophy (LVH) at baseline
- Main cause of heart failure (ischemic vs. non-ischemic or unknown)
- Start of first IMP dose prior to vs. after hospital discharge (or urgent care facility where appropriate)

For each factor, a marginal Cox proportional hazard model stratified by region and LVEF (note that when region is the subject of the analysis stratification will only be by LVEF; similarly when LVEF is the subject of the analysis, stratification will only be by region) with non-CV death as a competing event will be constructed, including the treatment, the factor, and the treatment-by-factor interaction terms as covariates. The treatment HR and CI will be estimated from this Cox model for each subgroup. P-values for interaction terms will be provided, and those <0.05 will be considered statistically significant and therefore suggestive of heterogeneity in the treatment effect. Results will be also presented by a forest plot.

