Heart failure can be divided into 2 or 3 main categories, depending on the region, based on measurement of the left ventricular ejection fraction (LVEF): HF with preserved ejection fraction (HFpEF; EF  $\geq 50\%$ ); heart failure with mid-range ejection fraction (HFmEF; LVEF  $\geq 40$  and  $< 50\%$ ); and heart failure with reduced ejection fraction (HFrEF;  $< 40\%$ ). Heart failure with mid-range ejection fraction is becoming a category of interest and was recently referenced in the 2016 European Society of Cardiology (ESC) Heart Failure Guidelines (9). The American Heart Association (AHA) guidelines refer to an intermediate category but do not label it HFmEF (10). A 2016 analysis of 99 825 admissions between January 2005 and September 2013 from 305 hospitals in the Get with the Guidelines-HF database showed the prevalence of HF as follows: 49% with HFrEF; 13% with HFmEF; and 38% with HFpEF (11).

The diagnosis of HF can be challenging in some patients since symptoms are nonspecific. Echocardiogram can help establish the diagnosis if the LVEF is  $< 40\%$ , classifying the patient into

the HFrEF category. HFmEF and HFpEF are more challenging to diagnose and elevated levels of natriuretic peptides (both b-type natriuretic peptide [BNP] and N-terminal B-type natriuretic peptide [NT-proBNP]) can aid in establishing the diagnosis. B-type natriuretic peptide and NT-proBNP are natriuretic peptides found in the heart. In response to volume overload and subsequent myocardial stretch, proBNP is secreted and then cleaved to NT-proBNP and BNP (12). The natriuretic peptides have been shown to predict clinical outcomes in clinical trials and have been used as surrogate markers of cardiovascular (CV) function. In a recent trial conducted in 149 patients with LVEF >45%, the PARAMOUNT trial, changes in NT-proBNP were used to compare the effect of sacubitril/valsartan with valsartan alone. The study showed that sacubitril/valsartan reduced NT-proBNP levels to a significantly greater extent (783 pg/mL at Baseline and 605 pg/mL at 12 weeks) compared with valsartan alone (862 pg/mL at Baseline and 835 pg/mL at 12 weeks) over 12 weeks (13).

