### 10.1.2.1 On-site Visit 2 (Day 1) Randomization

The Randomization Visit should occur prior to hospital discharge if applicable, or within 3 days after discharge from hospital, ED, HF unit, or infusion center.

The following procedures/assessments will be performed at Visit 2 (Day 1):

- Review of inclusion/exclusion criteria
- Measurement of body weight
- Vital signs (sitting BP, heart rate)
- AEs, including SAEs/AESIs/EOSIs (including severe hypoglycemia) and endpoint events (if any) are collected (if a renal endpoint relating to a reduction in eGFR is suspected, see [Section 9.1.2.1](#))
- Abbreviated physical examination, including lower extremities
- IRT to be contacted and Randomization will occur if the patient is eligible for the study
- IMP is dispensed
- Concomitant medications are assessed
  - It is **critical** that background medications at time of Randomization are accurately and fully captured
  - The dose of any concomitant RAAS inhibitors, ARNIs, MRAs, direct renin inhibitors, loop diuretics, and beta-blockers should be collected **at Baseline and at all study visits**. Where patients are receiving RAAS inhibitors, ARNIs, MRAs, loop diuretics, and/or beta-blockers at lower than the optimal/ maximally tolerated dose, the reason for this should also be recorded.
- Contact information is reviewed and updated if needed (address, email, home, and cell phone number) for patient, patient's family and patient's GP/cardiologist/diabetologist (as applicable, to be recorded in source documents). Alternate contact information for patients (ie, relative or friend) should also be reviewed as a backup
- The following laboratory testing:
  - NT-proBNP (before administration of study drug)
  - HbA1c
  - Hematology
  - Chemistry (including eGFR)
  - Lipids
  - Urine pregnancy testing for WOCBP (any positive urine test results must be confirmed by a serum pregnancy test)
  - [REDACTED]
  - [REDACTED]

- KCCQ-12 questionnaire
- An appointment for Visit 3 will be made

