## 11 STATISTICAL CONSIDERATIONS

### 11.1 DETERMINATION OF SAMPLE SIZE

The study is powered by primary endpoints of time to first occurrence of CV death or HHF in patients with LVEF <50%, and in the total patient population. In order to achieve the target number of events of 947 first occurrence of CV death/HHF in patients with LVEF <50% and 1341 first occurrences of CV death/HHF in the total patient population, it is estimated that approximately 4000 patients will be randomized over an estimated 29 months of recruitment period with approximately 3 months of follow-up after the last patient is randomized.

The sample size calculation is based on the following trial design assumptions:

- A recruitment period of approximately 29 months
- Approximately 3 months of follow-up after the last patient is randomized
- 29.2%, 39.7% and 44.5% event rate by Month 6, Month 12, and Month 24, respectively, in the placebo group (by assuming yearly hazard rate at Months 1, 2, 3, 4, 5, 6, 12, 24, and 36 be 1.06, 0.87, 0.74, 0.62, 0.49, 0.36, 0.32, 0.08, and 0.05, respectively)
- Hazard ratio (HR) = 0.81 for sotagliflozin versus placebo for patients with LVEF <50% and for patients with LVEF  $\geq$ 50%
- 2% annual censoring rate

This will provide:

- 90% power (with  $\alpha=0.05$ , 2-sided) to demonstrate superiority of the primary endpoint (first occurrence of CV death or HHF) comparing sotagliflozin versus placebo in patients with LVEF <50%.
- More than 90% power (with  $\alpha=0.05$ , 2-sided) to demonstrate superiority of the primary CV endpoint (first occurrence of CV death or HHF) comparing sotagliflozin versus placebo in the total patient population.

This is an event-driven study. Therefore, the study will continue until approximately 947 primary events (first occurrence of CV death or HHF) have been positively adjudicated in patients with LVEF <50%, AND approximately 1341 primary events (first occurrence of CV death or HHF) have been positively adjudicated in total patient population, and  $\geq$ 3 months follow-up for the last randomized patient.

Calculations were based log-rank test with user defined survival, accrual and drop-out rates by using EAST 6.4.

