## 1.3 DETERMINATION OF SAMPLE SIZE

The originally assumed sample size of 4,000 patients was based on a hazard ratio of 0.81 and the desire to examine effects in both the overall population and those with LVEF>50%. Given the early termination of SOLOIST, the study is not powered for these assumptions. However, an examination of efficacy is relevant because hazard ratios less than 0.81 have been reported with SGLT inhibition in stable heart failure, the potential for efficacy may differ in the setting of acute worsening of heart failure (where efficacy has not been examined to date), and the profile of sotagliflozin (with gastrointestinal SGLT1 inhibition in addition to SGLT2 inhibition) may differ from that of selective SGLT2 inhibitors. These analyses are conducted without any new sample size calculations.

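### The primary total-events model is valid, but by omitting baseline NT-proBNP it leaves a modest gain in precision, of uncertain size, unused

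*SAP*

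**What the plan says.** SAP 2.4.4.1 specifies a stratified Wald test, with the HR taken from a "marginal Cox proportional hazard model stratified by region and ejection fraction" and a robust sandwich variance. It adds: "This primary comparison will be a 2-sided test at the 0.05 type 1 error level". The listed sensitivity analyses are two on-treatment versions; none adjusts for a baseline covariate. SAP 2.4.4.2 applies the same method to the event-type secondary endpoints.

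Protocol 4.1 states: "The natriuretic peptides have been shown to predict clinical outcomes in clinical trials". It gives no strength of prediction. Protocol 6.1.2 schedules a central-laboratory NT-proBNP sample at Randomization before dosing, and the Visit 2 list in Protocol 10.1.2.1 includes "NT-proBNP (before administration of study drug").

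The SAP lists NT-proBNP among the baseline characteristics (2.1.1) and as a change-from-baseline endpoint (2.1.3.3). In the primary endpoint analysis it appears only as a subgroup factor split at the median (2.4.4.1).

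On power, SAP 1.3 says: "Given the early termination of SOLOIST, the study is not powered for these assumptions". No new sample size calculation is made.

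**The concern.** In a total-events analysis, differences in risk between patients inflate the robust variance of the log HR. A prognostic baseline covariate removes part of that excess and leaves the treatment ratio essentially unchanged. The protocol names such a covariate, and the sample is already scheduled.

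The omission sits oddly with the rest of the SAP. It concedes lost power, and Appendix D justifies total occurrences partly by their greater sensitivity. Section 2.4.4.2 adjusts the KCCQ-12 and eGFR analyses for baseline. The subgroup section already plans to put NT-proBNP into this same marginal model, but dichotomised and with an interaction.

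The testing order raises the stakes. Under SAP 2.4.4.3 no secondary endpoint supports an inference unless the primary is significant, so power on the primary carries through the whole confirmatory sequence.

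**Working it through.** **1. The plan's own figure.** Protocol 11.1 assumes "Hazard ratio (HR) = 0.81 for sotagliflozin versus placebo for patients with LVEF <50"% (and the same for LVEF ≥50%), two-sided alpha 0.05 and 90% power. Schoenfeld's formula for 1:1 allocation gives

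events = 4(1.960 + 1.282)² / (ln 0.81)² = 4 × 10.51 / 0.0444 ≈ 947.

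This matches the stated target. With 1341 events, power = Φ(½√1341 × 0.2107 − 1.960) = Φ(1.898) ≈ 97.1%, consistent with "More than 90% power". These figures apply to first events in the full-size trial. They do not describe the total-events analysis after the early stop.

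**2. Assumptions that the documents do not supply.** N = 1,200 (also 800 and 2,000); follow-up 0.1 to 1.8 years; 0.6 non-fatal events and 0.12 CV deaths per patient-year; residual between-patient (frailty) variance θ of 0.5 or 1.5; rate ratio of 1.2, 1.5 or 1.8 per SD of log NT-proBNP.

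**3. Simulation.** There were 1,500 trials per setting, with 10 region-by-LVEF strata, total events with CV death as a terminal counted event, a robust variance and a Wald test. Each trial was fitted with strata only and with the covariate added. Non-CV death was not simulated. Events averaged 589 to 685 in the settings tabulated.

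| HR | θ | Rate ratio per SD | Power, strata only | Power, adjusted | SE, strata only → adjusted | Squared SE ratio |
|---|---|---|---|---|---|---|
| 0.81 | 0.5 | 1.2 | 64.4% | 65.7% | 0.0883 → 0.0877 | 1.01 |
| 0.81 | 0.5 | 1.5 | 59.9% | 62.9% | 0.0921 → 0.0890 | 1.07 |
| 0.81 | 0.5 | 1.8 | 51.3% | 58.7% | 0.0973 → 0.0910 | 1.14 |
| 0.81 | 1.5 | 1.2 | 46.5% | 47.4% | 0.1067 → 0.1063 | 1.01 |
| 0.81 | 1.5 | 1.5 | 41.1% | 43.7% | 0.1107 → 0.1085 | 1.04 |
| 0.81 | 1.5 | 1.8 | 33.7% | 37.7% | 0.1160 → 0.1118 | 1.08 |
| 0.70 | 0.5 | 1.2 | 96.6% | 96.6% | 0.0909 → 0.0902 | 1.02 |
| 0.70 | 0.5 | 1.5 | 94.9% | 96.1% | 0.0948 → 0.0917 | 1.07 |
| 0.70 | 0.5 | 1.8 | 91.9% | 96.3% | 0.0998 → 0.0936 | 1.14 |
| 0.70 | 1.5 | 1.2 | 87.1% | 87.4% | 0.1088 → 0.1084 | 1.01 |
| 0.70 | 1.5 | 1.5 | 82.2% | 83.9% | 0.1128 → 0.1107 | 1.04 |
| 0.70 | 1.5 | 1.8 | 75.1% | 79.3% | 0.1183 → 0.1140 | 1.08 |

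The squared SE ratio minus one is the equivalent increase in patients: about 1 to 2%, 4 to 7% and 8 to 14% at rate ratios of 1.2, 1.5 and 1.8. The estimated HR hardly moved; the largest shift was 0.714 to 0.707.

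**4. Hand check at 1.5 per SD.** Let μ be events per patient and b = ln 1.5, so exp(b²) − 1 = 0.179. With equal follow-up and no terminal event, the unadjusted variance is proportional to 1 + μ[(1 + θ)exp(b²) − 1], and adjustment removes μ[exp(b²) − 1].
- θ = 1.5, μ = 635/1200 = 0.529: 0.0946 / 2.030 = 4.7%.
- θ = 0.5, μ = 677/1200 = 0.564: 0.1008 / 1.433 = 7.0%.

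The simulated reductions are 1 − (0.1085/0.1107)² = 3.9% and 1 − (0.0890/0.0921)² = 6.6%.

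**5. Other settings** (rate ratio 1.5 per SD, θ = 1.5).
- HR 0.70, N = 800: power 64.6% to 67.0%.
- HR 0.70, N = 2,000: power 96.0% to 96.6%.
- HR 0.70, N = 1,200, 5% of values missing and mean-filled: 81.3% to 83.9%.
- No effect, N = 1,200: rejection 6.5% without and 6.2% with the covariate (Monte Carlo SE about 0.6 points). Adjustment adds no error, but both rates are slightly above 5%, so the powers above are not size-corrected.

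**6. Single-event endpoints.** A Cox model for one terminal event was simulated with N = 1,200, about 110 deaths, HR 0.81 and 0.70, ratios of 1.3 to 1.8 per SD and 1,000 trials per setting. The adjusted-to-unadjusted SE ratio was 1.001 throughout. Power changed by −0.3 to +2.8 points, mostly within simulation noise.

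**The case against.** The strongest case for leaving the model alone is that it is already coherent. It stratifies by exactly the two randomization factors, as Protocol 11.4.2.1 did, and the test is valid. That stands.

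The size of the gain cannot be read from the documents. The statement in Protocol 4.1 is general background. I 09 (Protocol 7.1.2) requires BNP of at least 150 or NT-proBNP of at least 600 pg/mL, with thresholds three times higher in atrial fibrillation, which may narrow the covariate's range. If NT-proBNP correlates with LVEF or region, the strata already absorb part of the gain. These points stand, and they are why only a range is given.

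A reader might infer that every patient has a usable value. The documents give a schedule and not completeness. Local-laboratory values are excluded from analysis (Protocol 9.2.2), so a missing central value may not be recoverable. A reader might also carry the argument to all event-type secondaries. Step 6 shows that it fails for CV death and all-cause mortality: the SE does not shrink, and the adjusted HR becomes conditional on the covariate.

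The SAP already makes several late changes, and another has some cost in credibility. The choice of NT-proBNP over NYHA class or eGFR can also be questioned. Neither point is decisive. The SAP says its choices were made blinded, the unadjusted HR would still be reported, and NT-proBNP is the marker that the protocol itself singles out as predictive.

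**Conclusion.** The point holds as a missed efficiency in the primary and other total-occurrence analyses. At N of about 1,200 the gain is about 0 to 1 power point for a weak predictor (1.2 per SD), 1 to 3 points at 1.5, and about 4 to 7 points at 1.8. This depends on the assumed event rates, frailty variance and prognostic strength, and I 09 may make it smaller.

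A reader might infer that the planned test is biased or invalid, or that a known amount of power has been lost. The documents support neither. Randomization and the robust variance make the unadjusted test valid, and no stated figure fixes the size of the loss.

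**What to change.** Before unblinding, amend SAP 2.4.4.1 and 2.4.4.2 as follows:
- Add log baseline NT-proBNP as a linear covariate to the stratified marginal model for the primary and the other total-occurrence endpoints. Keep the region and LVEF strata.
- Name the central-laboratory Randomization value as baseline. SAP 2.1.1 already defines laboratory baselines this way, but the general efficacy definition in SAP 2.5.3 differs.
- Fill a missing value with the overall mean and add a missing indicator, so that no ITT patient is dropped.
- Report the unadjusted stratified HR as a sensitivity analysis.
- Leave CV death and all-cause mortality unadjusted in the main analysis.

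No new data are needed. The cost is a short missing-value rule and one more late, blinded change to the SAP. The text should also say whether the 240-day, on-treatment and subgroup models carry the covariate, since NT-proBNP is already a subgroup factor.

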#### **4.4 RATIONALE FOR CURRENT STUDY**

The main objectives of the study are to demonstrate whether sotagliflozin reduces the composite of CV death and HHF as compared to placebo in diabetic patients after admission for WHF.

In all patients, double-blind treatment (sotagliflozin or placebo) will be added to the standard of care, evidence-based background therapies for their underlying diabetes and HF conditions.

The randomization will be stratified according to LVEF (<50% or ≥50%) since they represent 2 distinct forms of HF. However, both forms lead to significant congestion and have the potential to be improved by an agent such as sotagliflozin.

Although ACE-i, beta-blockers and MRAs are recommended in patients with HFrEF to reduce the risk of HFrEF and death, they have failed to reduce mortality in patients with HF and preserved EF. Therefore, in order to evaluate the effect of sotagliflozin on patients across the spectrum of LVEF values, there are 2 primary endpoints. The first in patients with a LVEF <50% and the second in the total patient population. The cut-off of 50% was chosen to group HFrEF and HFmEF patients (a very small subgroup, 13% [11]) together, since HFmEF patients are a category of interest.

In order to do a robust analysis of the potential improvement in patients with LVEF <50%, recruitment will begin with all patients (LVEF <50% and LVEF ≥50%). Enrollment of patients with LVEF ≥50% will be capped at ~27% of the total patient population and enrollment of patients with LVEF <50% will continue to reach the total patient population. In addition, since an intermediate category has recently emerged (LVEF between 40% and 49%) for which little information on outcome is available, an exploratory subgroup analysis will also be performed using the 3 categories (<40%, 40 to 49% and ≥50%).

In addition, since this patient population is burdened with repeated hospitalizations and visits to the emergency department (ED) or HF acute unit (where available) with major financial consequences for healthcare systems and utilization of public health care resources, the study will also assess, in addition to the occurrence of a primary event, the occurrence of the total number of CV deaths and HFrEF or urgent HF visits (see [Appendix B](#)) throughout the course of the study. Finally, the effect of sotagliflozin on CV death alone and all-cause mortality will be analyzed.

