### Appendix D Key Changes to Original Planned Analysis and Protocol

Change	Rationale
Primary endpoint analyzes total occurrences (first and potentially subsequent) rather than first occurrence	Total occurrences are expected to be a more sensitive indicator of treatment benefit, are clinically relevant to patients with heart failure, and have been sensitive to change in several cardiovascular outcomes trials
Primary endpoint adds urgent HF visit to original planned endpoint of CV mortality and HHF	Urgent HF visits are clinically relevant and can be reduced by effective treatment
All event endpoints based on investigator reporting rather than adjudication	Adjudication was not completed, and investigator-reported events are clinically relevant
Only one primary objective is applied to the overall population: initially there were co-primary objectives, one to demonstrate reductions in CV morbidity and mortality in those with LVEF<50%, and one to demonstrate reductions in CV morbidity and mortality in the overall population	Primary focus is on overall population rather than subgroups
Composite renal endpoint was moved from a secondary objective to other objective; change in eGFR over time was added as a secondary benefit	Given the current follow-up in SOLOIST, change in eGFR over time is a more sensitive measure of renal benefit than the composite renal endpoint
Addition of ARR, DAOH and PDAOH as other endpoints	ARR provides a perspective of treatment benefit, and DAOH and PDAOH capture clinical relevance of decreased hospitalizations
Hypoglycemia safety moved to efficacy endpoint	Reductions in hypoglycemia have been seen with sotagliflozin in both type 1 diabetes and T2D, indicating the value of statistical analyses of hypoglycemia results
CV death and HHF in patients with LVEF <50%, with and without T2D (a secondary endpoint in Amendment 2) is not included in current analysis plan	Limited enrollment after Amendment 2 means subgroup analysis of those without T2D is not adequately powered for a secondary endpoint
All-cause mortality was a secondary endpoint in the original protocol, moved to “other	Original move to “other endpoint” was based on FDA feedback that it would not be included

endpoint” in Protocol Amendment 2, and returned to a secondary endpoint in this analysis plan	in labeling, but it was returned to secondary endpoint because of its high clinical relevance

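### SAP 2.4.4.1 tests effect modification by LVEF, age, eGFR, BMI and NT-proBNP only on grouped values; adding a prespecified continuous interaction would recover information at little cost

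*SAP*

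**What the plan says.** The subgroup list in SAP 2.4.4.1 gives each of the five numeric modifiers in grouped form only: LVEF at 50%, and again at 40% and 50%; age at 65; eGFR at 60; BMI at 30; and "NT-proBNP (≤Median, >Median". For each listed factor it fits a stratified marginal Cox model "including the treatment, the factor, and the treatment-by-factor interaction terms as covariates". When LVEF is the factor, stratification is by region alone. The reading rule is: "P-values for interaction terms will be provided, and those <0.05 will be considered statistically significant and therefore suggestive of heterogeneity". Subgroup hazard ratios with confidence intervals go on a forest plot.

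SAP 2.1.1 lists age in years, LVEF in per cent, and eGFR, BMI and NT-proBNP as measured values, so the uncut data exist. Protocol 11.4.2.1 names the subgroup variables and leaves the details to the SAP.

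Protocol 4.4 gives the reason for two primary endpoints: "in order to evaluate the effect of sotagliflozin on patients across the spectrum of LVEF values". The same section promises an exploratory analysis in three LVEF categories. SAP Appendix D removes the LVEF <50% co-primary objective, with the rationale "Primary focus is on overall population rather than subgroups".

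**The concern.** Cutting a numeric modifier treats everyone on one side of the cut as alike. If the treatment effect changes gradually with LVEF, eGFR or NT-proBNP, that discards information the test could use and makes the gradient easier to miss. The model already has the right form, so entering the factor uncut needs no redesign.

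The trial has little power to spare for interactions. Enrolment closed before the planned 4,000 patients (SAP 1.1), and SAP 1.3 says the study is not powered for its original assumptions. At stake is how well the exploratory analyses can show whether benefit varies across patients, particularly by LVEF. The test of the primary endpoint is not at stake.

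The documents describe the 40% and 50% LVEF boundaries as heart-failure classes and stratify randomization at 50%. They give no reason for the age, eGFR, BMI or NT-proBNP cuts.

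**Working it through.** **The plan's own figure.** The documents give no power for any interaction test. Their power figure is for the original first-event endpoint in LVEF <50% (protocol 11.1): 947 events, HR 0.81, two-sided 0.05, 90% power. Schoenfeld's formula gives 4 × (1.960 + 1.282)² / (ln 0.81)² = 947, so it reproduces.

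**Inputs.**
- Interaction threshold: 0.05 per factor (SAP 2.4.4.1).
- NT-proBNP split: 50/50 by definition.
- Planned share with LVEF ≥50%: about 27% (protocol 4.4), or 1100/4000 = 27.5%.
- Registry mix of 49/13/38% for LVEF <40, 40 to <50 and ≥50 (protocol 4.1), used only to place the 40% cut.
- Assumed, not in the documents: the modifier is normal (NT-proBNP on the log scale) and its effect is linear on the log-HR scale.

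**Formula.** Information kept by grouping is the between-group variance of the modifier divided by its total variance. For two groups with share p in one of them, this is φ(z_p)² / [p(1−p)].

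- Median split: 0.3989² / 0.25 = 0.637, a loss of 36%.
- LVEF at 27.5%: 0.3337² / (0.275 × 0.725) = 0.558, a loss of 44%. At 27% the loss is 44.5%.
- Other splits: 60/40 loses 38%, 70/30 loses 42%, 75/25 loses 46% and 80/20 loses 51%.

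For three groups, information kept is the sum over groups of [φ(lower cut) − φ(upper cut)]² / p. Placing the registry's 49:13 ratio within the 72.5% below LVEF 50% gives shares of 57.3/15.2/27.5%, and 0.268 + 0.023 + 0.405 = 0.696, a loss of 30%. The raw registry mix loses 29%.

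**Power.** If the continuous test has expected z of 1.960 + z_power, the two-group test has power Φ(√kept × (1.960 + z_power) − 1.960).

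| Continuous test | Median split | LVEF at 27.5% |
|---|---|---|
| 90% | 73% | 68% |
| 80% | 61% | 55% |
| 50% | 35% | 31% |
| 20% | 14% | 13% |

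Three-group LVEF uses a 2-df test. When the continuous test has 80% power, it has 54% (57.3/15.2/27.5) or 55% (49/13/38), against 55% and 59% for two groups at the same 50% cut. The information gained from the third group does not become power.

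**Simulation check.** Cox models on first events were simulated with an assumed 1,500 patients, an interaction of 0.25 per SD and 150 trials per split. Mean z fell from 3.51 to 2.77 at 50/50, a loss of 1 − (2.77/3.51)² = 38%. It fell from 3.53 to 2.69 at 72.5/27.5, a loss of 42%. Both are close to the formula.

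**Sensitivity to the assumptions.** A uniform modifier loses 25% at the median and 40% at 72.5/27.5. A log-normal modifier (log SD 1, assumed) acting linearly on its raw scale loses 73% at the median. If the effect is a step exactly at a median cut, grouping loses nothing and the linear term loses 36%.

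**The case against.** The strongest defence is that the LVEF cuts belong to the design. Protocol 4.4 treats LVEF below and above 50% as distinct forms of heart failure, randomization is stratified there, and the three-category analysis is promised in advance. If the effect follows those classes, the grouped test is the better one. This stands, and it is why the planned tests should not be replaced. A trend p-value also does not test the hazard ratios shown on the forest plot.

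Some stronger readings are tempting but unsupported:

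- A reader might infer a 36–45% loss for all five factors. The documents give no splits for age, eGFR or BMI; three-group LVEF falls outside that range; and the LVEF figure rests on the planned cap, with the achieved split unknown after early closure.
- A reader might infer that the LVEF interaction p-value now stands in for the dropped co-primary. The sentence on the spectrum of LVEF introduces the two grouped primary endpoints, and the SAP still reports a hazard ratio and interval for LVEF <50%, now for its revised primary endpoint.
- A reader might infer that a non-significant interaction will be reported as a uniform effect. The SAP says only what p<0.05 suggests. It gives no rule for the opposite result, and the three-group forest plot could show a gradient.

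It is also fair that absolute power losses depend on the starting point. If the continuous test has only 20% power, the loss is 6–7 points and neither test is informative.

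**Conclusion.** The point holds as a cheap improvement to an exploratory analysis. It is not an error or a contradiction in the plan. The five modifiers are tested only in grouped form. For a roughly normal modifier with a linear effect on the log-HR scale, this loses about 36% of the interaction information at a median split and about 44% for two-group LVEF at the planned cap. Three-group LVEF loses about 30% with no net gain in power. No figure can be given for age, eGFR or BMI without their splits, and the loss is zero if the effect is a step at the cut.

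The fixed sequence in SAP 2.4.4.3 covers only the primary and secondary endpoints, and protocol 11.4.2.4 describes subgroup p-values as nominal and descriptive. The primary conclusion therefore does not depend on this point.

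**What to change.** In SAP 2.4.4.1, keep all listed categories, their hazard ratios, their interaction tests and the forest plot, including the three-category LVEF analysis. Add, before unblinding, a treatment-by-continuous-covariate interaction for LVEF, age, eGFR, BMI and log NT-proBNP. Use the same stratified marginal Cox model with robust variance, stratified by region only when LVEF is the factor. Prespecify a spline check of linearity and a plot of the treatment hazard ratio, with its confidence band, against LVEF. Label all of this exploratory.

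The cost is SAP wording, five model fits on data already collected, and the spline checks. The downsides are a linearity assumption and five more nominal p-values outside the type I error hierarchy. The list rises from 19 interaction tests to 24, so the number expected below 0.05 by chance goes from 19 × 0.05 = 0.95 to 24 × 0.05 = 1.2.
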